5.7.1. Permitted medications

Patients should receive medication appropriate to their health condition during the whole study.

During the period starting with administration of each dose of study treatment and ending 30 days after the administration of each dose, concomitant medications administered for the treatment of an AE must be recorded in the CRF with generic name of the medications (trade names are allowed for combination drugs only), medical indication (including which AE), total daily dose, route of administration, start and end dates of treatment. Similarly, concomitant medications administered for the treatment of a SAE, at any time, must be recorded on the SAE screens in the CRF, as applicable (Refer to Section 8.2 for the definition of a SAE).

5.7.2. Prohibited medications or non-drug therapies

Patients may not receive concomitant treatment during the study with any of the following:

CONFIDENTIAL

- a. Investigational or non-registered product for melanoma other than the recMAGE-A3 + AS15 ASCI ± Poly IC:LC.
- b. Other anticancer treatments, including but not exclusively, chemotherapeutic, immunomodulating agents and radiotherapy.
- c. Chronic use (more than 7 consecutive days) of systemic corticosteroids or any other immunosuppressive agents.

The use of prednisone, or equivalent, < 0.125 mg/kg/day (absolute maximum 10 mg/day), inhaled corticosteroids or topical steroids is permitted.

- d. Administration of a vaccine not foreseen by the study protocol during the period within the prohibited time as specified in Section 5.8.3.
- e. Repetitive administration of immunoglobulins and/or any blood products during the study period.

Any of these specifically contraindicated treatments and/or medications administered at any time during the study period are to be recorded in the CRF with generic name of the medications (trade names are allowed for combination drugs only), medical indication, total daily dose, route of administration, start and end dates of treatment.

If any of these is taken, it will require either permanent discontinuation of study treatment (see Section 5.2.1.2) or may determine a patient's evaluability in the according to protocol (ATP) analysis (see Section 10.3.1 for definition of study populations to be evaluated).

5.7.3. Time-window for prophylactic vaccination against infectious diseases

Immunization with any commercial anti-infectious vaccine may be performed during the study. However, this may not take place during the period from 7 days before any study treatment administration to 7 days after it. Thus, if the study treatment is to be given on a notional Day 0, then immunization with any commercial vaccine may be performed on or before Day -8, and on or after Day 8.

Any commercial vaccine administered in the period beginning 30 days preceding each dose of study treatment and ending one month (minimum 30 days) after each dose of study treatment is to be recorded with trade name, route of administration and date(s) of administration.

Any investigational medication or treatment administered throughout the study period (i.e., from Day 0 through Visit 13) must be recorded in the CRF.

6. STUDY ASSESSMENTS AND PROCEDURES

6.1. General study aspects

6.1.1. Attendance for study visits

It is the investigator's responsibility to ensure that the intervals between visits/contacts are strictly followed.

The timing for study visits can be found in Section 6.2. Permitted deviations from the stipulated date of visit (due e.g., to week-ends or public holidays) will be as follows:

Induction phase \pm 4 calendar days.

Maintenance and follow-up phases \pm 14 calendar days.

In case of deviations exceeding these limits, the sponsor, MCC will decide whether the violation is to be regarded as:

- A minor violation (i.e., without consequence),
- A major violation (resulting in exclusion of the patient from the population of patients evaluable according to protocol).

When a study treatment has to be postponed (refer to Section 5.2.1.1 for details on postponement of study treatment), the next study visit should be planned at a time allowing:

- A minimum of 14 days between 2 treatment administrations,
- To keep up with the schedule as based on the date of first study treatment administration (Visit 1).

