patients in the adjuvant and metastatic settings, respectively, are very similar, so it is reasonable to expect that an equivalent tumor response might be seen in the adjuvant melanoma setting.

Taking into account the tumor-specificity of recMAGE-A3, the MAGE-A3 antigen expression levels in stage IV melanoma tumors, the acceptable tolerability of the recMAGE-A3 + AS15 ASCI and the promising results from Phase II proof-of-concept trials (GSK 249553/008 and 249553/004), this Phase II trial will evaluate the immunogenicity of the recMAGE-A3 + AS15 ASCI with or without the toll-like receptor (TLR) agonist Poly IC:LC (Hiltonol) as adjuvant therapy for MAGEA3-positive patients with resected stage IV melanoma that have been rendered free of disease but are at very high risk of relapse.

Objectives:

Primary Objectives:

- To evaluate the safety and tolerability of recMAGE-A3 + AS15 ASCI compared to recMAGE-A3 + AS15 ASCI in combination with Poly IC:LC in patients with resected stage IV melanoma.
- To evaluate the immunogenicity of recMAGE-A3 + AS15 ASCI compared to recMAGE-A3 + AS15 ASCI in combination with Poly IC:LC as measured by humoral response (antibodies serum titers) in patients with resected stage IV melanoma.

Secondary Objectives:

- To evaluate the clinical activity of the recMAGE-A3 + AS15 ASCI compared to recMAGE-A3 + AS15 ASCI in combination with Poly IC:LC in terms of relapse-free survival (RFS) and overall survival (OS) in the overall study population.
- To evaluate the immunogenicity of the recMAGE-A3 + AS15 ASCI compared to recMAGE-A3 + AS15 ASCI in combination with Poly IC:LC measured by T cell responses against MAGE-A3 antigen.
- To assess the gene profile of tumor tissue in the two study arms and evaluate the activity of the recMAGE-A3 + AS15 ASCI +/- Poly IC:LC in terms of RFS in the sub-population of patients presenting a potentially favorable gene signature (see Section 6.4.4), and in the sub-population of patients without this gene signature.

Translational Research Objectives:

- Translational research includes assessment of MAGE-A3 expression of tumor tissue from recurrent lesions, and gene profiling of recurrent or new lesions.

Study design:

- Experimental design: Two-arm, open, randomized single center study.
- Treatment allocation: Patients will be randomized (1:1 ratio) to receive either recMAGE-A3 + AS15 ASCI or recMAGE-A3 + AS15 ASCI in combination with Poly IC:LC.
- Blinding: None, open label.

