10.5. Elimination criteria for analysis

As defined in Section 5.8.2, certain medications are prohibited during this study. Among those medications, the following will not require withdrawal of the patient from the study but may determine the patient's evaluability in the according-to-protocol (ATP) analysis.

- Chronic administration of immunosuppressants or other immune-modifying drugs during the study period. The use of prednisone, or equivalent, < 0.125 mg/kg/day (absolute maximum 10 mg/day), inhaled corticosteroids or topical steroids is permitted.
- Administration of a vaccine not foreseen by the study protocol during the prohibited time period as specified in Section 5.8.3.
- Repetitive administration of immunoglobulins and/or any blood products during the study period.

Patients to be excluded from the ATP populations will be identified during a review of data.

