10.7.4. Analysis of immunogenicity

The analysis of immunogenicity will be performed on the ATP population, cf. Section 10.4.3.

The immunogenicity induced by the recMAGE-A3 + AS15 +/- poly IC:LC ASCI will be assessed through calculation of the geometric mean titres (with 95% CI), the proportion of seropositive patients and antibody response in the two treatment groups. This will be done for antibodies at baseline, after 2, 4, 6, 7, and 9 dose administrations and post-treatment (i.e., at the concluding examination at Visit 14, 3 months after the injection of dose 13, cf. Section 6.3).

Antibody titres may also be investigated using reverse cumulative curves.

A possible correlation between the immunological response (such as antibody response to MAGE-A3) and RFS may be explored using a time-dependent Cox model.

The immunogenicity will also be evaluated in the gene signature-positive and gene signature negative populations, separately.

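### A major visit-timing violation excludes the whole patient from the ATP set, so a later deviation can remove antibody titres that were drawn on schedule

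*Combined protocol and SAP*

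**What the plan says.** Section 6.1.1 sets visit windows of ±4 days in induction and ±14 days in maintenance and follow-up. Outside them, "In case of deviations exceeding these limits, the sponsor, MCC will decide whether the violation is to be regarded as" one of two things: "A minor violation (i.e., without consequence"), or "A major violation (resulting in exclusion of the patient from the population of patients evaluable according to protocol"). No criteria separate the two, and no outcome removes only the affected visit or sample.

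Section 10.7.4 states: "The analysis of immunogenicity will be performed on the ATP population", and refers to Section 10.4.3. Antibody titre is a primary endpoint and the basis of the sample size in Section 10.3.

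Other grounds also act on the patient:
- Section 5.7.2 says that a prohibited treatment, where it does not require permanent discontinuation, "may determine a patient's evaluability in the according to protocol (ATP) analysis". Section 10.5 lists the relevant categories.
- Section 10.4.3 gives early discontinuation of treatment as an example of a major deviation.
- Section 10.5 adds: "Patients to be excluded from the ATP populations will be identified during a review of data".

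The only rule at the level of a single measurement, in Section 10.6.2, covers missing or non-evaluable results. The Synopsis states "Blinding: None, open label", and Appendix A gives the sponsor as the single study centre.

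**The concern.** A titre drawn on time at week 6 or week 12 cannot be affected by a visit that slips in year 3. Under Section 6.1.1, that later slip, if graded major, still takes the patient out of the set on which the titre is analysed. Membership of an early comparison is then decided by what happens after the sample: how long the patient keeps attending, whether treatment stops, and which other treatments are given. Each of these may differ by arm, so the comparison is no longer protected by randomization even for samples that were complete and correctly timed.

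Two features make this worse. The minor-or-major decision has no criteria and is taken by a party that knows the arm. The text also does not settle whether the ATP set carries the main immunogenicity result.

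What is at stake is precision on an endpoint planned at only 62% power, together with a selection effect of unknown sign.

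**Working it through.** **1. Visits that can trigger the rule.** After Visit 5 (week 12) a fully followed patient has 14 scheduled visits: Visits 6 to 14 (9) and F1 to F5 at months 36 to 60 (5). Table 8 schedules humoral samples at Visits 1, 3, 5, 7, 8, 10 and 14 and at F2. Of the 14 later visits, 5 have an antibody sample (7, 8, 10, 14, F2) and 9 have none. All 14 fall under the window rule. Section 6.4.2 also ends collection of immunology samples on October 1, 2015, while analysis of existing samples continues, so visits after that date bring no new titre but can still cost old ones.

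**2. The plan's own power.** Inputs from Section 10.3: geometric means 7,000 and 10,500, SD 0.28 on the log scale, 20 per arm, one-sided 0.05. Base 10 is an inference; it reproduces the plan's figures.
- Difference: log10(10,500/7,000) = 0.1761.
- Noncentrality: 0.1761 / (0.28 × √(2/n)).
- n = 20: noncentrality 1.989, 38 df, critical t 1.686, power 62.1%. The stated 62% is reproduced.

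**3. Power after equal loss in both arms.**

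| n per arm | Noncentrality | df | Power |
|---|---|---|---|
| 20 | 1.989 | 38 | 62.1% |
| 18 | 1.887 | 34 | 58.1% |
| 16 | 1.779 | 30 | 53.7% |

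The enrolment of up to 44 allows for about 10% loss to follow-up. It makes no allowance for ATP exclusions.

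**4. How many patients might be lost.** The documents give no rate of major violations. Assume a rate q per visit, and exponential RFS with the plan's medians of 12 and 24 months. A patient attends the k-th of the 14 visits, at month t(k), if still relapse-free, with probability S(t) = exp(−ln 2 × t / median). The chance of exclusion is then the sum over k of S(t(k)) × q × (1 − q)^(k − 1).

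| q | Expected exclusions of 20, median 12 months | Expected exclusions of 20, median 24 months | Risk if relapse-free to month 60 |
|---|---|---|---|
| 2% | 1.4 | 2.5 | 1 − 0.98^14 = 25% |
| 5% | 3.3 | 5.4 | 1 − 0.95^14 = 51% |

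For a patient who relapses before month 60, the risk is 7% (12-month median) or 10% (24-month median) at q = 2%, and 15% or 22% at q = 5%. The mean loss over the two arms is about 2 and 4 patients, which is why step 3 uses those values.

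**5. Direction.** From the timing rule alone, risk rises with relapse-free follow-up, because Section 6.3.10.2 ends clinic follow-up visits after relapse. Early discontinuation works the other way: Section 5.2.1.2 requires treatment to stop at relapse, so that ground removes relapsed patients. The documents give nothing from which to net the two.

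**6. Limit of the power figures.** Section 10.3 places its effect and SD at about 6 months, and steps 2 and 3 keep the planned 20 per arm. If relapsed patients gave no sample at week 36 (8.28 calendar months), the same RFS model would leave 20 × 0.620 = 12.4 and 20 × 0.787 = 15.7 patients, with power near 49% before any timing exclusion. The fall from 62% is therefore an illustration against the planned figure, not a forecast for week 36.

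**7. Windows against postponement.** Section 5.2.1.1 allows a maintenance dose to be postponed by up to 3 months. Section 6.1.1 treats a maintenance visit more than 14 days off schedule as a violation to be graded. The same visit can be permitted by one section and graded major under the other.

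**The case against.** Four points on the other side have force.

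**Exclusion is not automatic.** A reader might infer that any late visit deletes titres. It does not: the sponsor must grade it major, and a late visit without an antibody sample could well be graded minor. Prohibited medication likewise only may affect evaluability. Nor does any vaccine in the study period count, since Section 5.7.3 bars commercial vaccines only from 7 days before to 7 days after a dose. This stands, and limits the point to what the text permits.

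**ATP may not be the main set.** Section 10.4.2 makes the Total Treated Population the set for data analysis, and Section 10.4.3 describes its own analyses as secondary and optional. The titres stay in the Total Treated set. But 10.4.2 is headed for efficacy, 10.4.3 names immunogenicity in its heading, and 10.7.4 assigns immunogenicity to ATP outright. The conflict is itself a reason to amend.

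**Long-term relapse-free patients are not shown to be the main losers.** It is tempting to conclude that they are, with a known bias between arms. The higher risk per patient holds for the timing rule taken alone. By count, at q of 2% to 5%, patients relapse-free at month 60 are only 10% to 11% (12-month median) or 34% to 35% (24-month median) of those excluded, and the early-discontinuation ground pulls the other way. The directional reading is not supported.

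**Biased grading is only a possibility.** Titres are measured by the collaborating company or a contracted laboratory, and nothing says that the grader sees them. The arm, however, is known to the sponsor, and nothing requires grading to finish before titres are available.

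**Conclusion.** The point holds as a gap in the rules for the ATP set. As written, a later deviation can remove earlier valid titres from the immunogenicity analysis named in Section 10.7.4, through an ungoverned decision taken with knowledge of the arm. Selection then depends on events after sampling that may differ by arm, and the net direction of any bias is uncertain. The size depends on a violation rate that the documents do not give. Equal loss of 2 to 4 patients per arm from 20 lowers power from 62% to about 58% to 54%, under the plan's effect, SD and one-sided 0.05. If the Total Treated set is confirmed as primary for immunogenicity, the effect is confined to a secondary analysis.

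**What to change.** - **Sections 6.1.1, 10.4.3 and 10.5:** define ATP membership for each time point. A timing violation removes only the titre drawn at that visit. A disqualifying medication or early discontinuation affects only titres drawn after it. A visit without a humoral sample cannot cause exclusion from immunogenicity.
- **Grading:** write the criteria for a major violation in advance. Grade from a listing without arm or titre, and finalise it before antibody results are merged.
- **Sections 10.4.2, 10.4.3 and 10.7.4:** name one primary immunogenicity population and label the other as supportive.
- **Sections 5.2.1.1 and 6.1.1:** reconcile the postponement of up to 3 months with the ±14-day maintenance window, so that it is clear how a permitted delay is classed.

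The cost is protocol and analysis-plan wording, with no added visits or samples. The drawback is that the number analysed differs by time point and must be shown in every immunogenicity table.

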6.2. Outline of study procedures

6.2.1. Induction phase

The first administration of study treatment (Visit 1) will take place a maximum of 12 weeks after surgical resection of the tumor.

CONFIDENTIAL

Study phase:	INDUCTION (V1-V5)						
			max. 12 w after resection	-	-	-	-
Time with respect to resection							
Study visit no.	S1 ^a	S2	1	2	3	4	5
Study treatment administration no.			1	2	3	4	5
Time after first study treatment administration			0	3 w	6 w	9 w	12 w
Informed consent	● ^a						
MAGE-A3 expression analysis ^b	●						
Inclusion and exclusion criteria	●	●					
Medical history	●	●					
Patient randomized		●					
Efficacy assessments							
Neck, chest, abdomen and pelvic CT scans		●					●
Brain MRI scan		● ^c	c	c	c	c	c
Physical examination	●	●	●	●	●	●	●
Safety assessments							
Adverse events recorded			●	●	●	●	●
pIMD recorded			●	●	●	●	●
Serious adverse events recorded		● ^e	●	●	●	●	●
Laboratory assays							
Blood samples taken for:							
Haematology	●	●					●
Blood chemistry	●	●					●
Blood samples taken for							
Humoral immunity ^d			●		●		●
Leukapheresis for cellular immune assays			●				●
Cellular immune assays ^h			●				●
Pregnancy test (for female patients) ^{f,g}		●	●	g	g	g	●
Investigational product							
Criteria for permanent stopping or postponement of study treatment				●	●	●	●
Recording of concomitant medications			●	●	●	●	●
recMAGE-A3 + AS15 +/- Poly IC:LC administration			●	●	●	●	●

w = weeks. Pts = patients.

- a. Since fresh tissue is to be used, the informed consent must be signed before surgery.
- b. MAGE-A3 screening must be performed on tissue removed during surgical resection. For the rapidity of testing and quality of the slides, tissue should be analyzed as soon as possible after operation. Part of the tissue will be used for the predictive gene list associated to treatment. Only tumor tissue from patients likely to meet all inclusion criteria should be sent for testing.
- c. Brain MRI scan performed up to 4 weeks before treatment. As an alternative, brain CT is allowed if an MRI is contraindicated.
- d. 10 mL of blood sample taken for examination of humoral immunity.
- e. SAEs related to study participation and concomitant medications should be recorded.
- f. A pregnancy test must be performed every 3 months for female patients of childbearing potential.
- g. A pregnancy test should be performed at any time during the study if the investigator/patient suspects that pregnancy has occurred.
- h. Eight green tops totalling 70 mL of blood for PBMC will be taken in patients who agree on days 1, 3, 7, 14 and 21 after the first and 5th treatments for assays of cellular immunity

Note: ● is used to indicate a study procedure that requires documentation in the individual CRF. ○ is used to indicate a study procedure that does not require documentation in the individual CRF.

Table 5. Timing of study visits and the assessments to be performed (Induction Phase)

6.2.2. Maintenance phase

Study phase:	MAINTENANCE (V6-V13)								Concluding visit
Study visit no.	6	7	8	9	10	11	12	13	14 ^a
Study treatment administration no.	6	7	8	9	10	11	12	13	-
Weeks after 1. study treatment administration	24	36	48	60	72	84	96	108	120
Months after 1. study treatment administration	6	9	12	15	18	21	24	27	30
Efficacy assessments									
Neck, chest, abdomen and pelvic CT scans	•	b	•	b	•	b	•	b	•
Physical examination	•	•	•	•	•	•	•	•	•
Safety assessments									
Adverse events recorded	•	•	•	•	•	•	•	•	•
pIMD recorded	•	•	•	•	•	•	•	•	•
Serious adverse events recorded	•	•	•	•	•	•	•	•	•
Laboratory assays									
Blood samples taken for:									
Haematology			•				•		•
Blood chemistry			•				•		•
Humoral immunity		•	•		•				•
PBMC for cellular immune assays		•			•		•		•
Pregnancy test (for female patients) ^{c, d}	•	•	•	•	•	•	•	•	•
Investigational product									
Criteria for permanent stopping or postponement of study treatment	•	•	•	•	•	•	•	•	
Recording of concomitant medications	•	•	•	•	•	•	•	•	•
recMAGE-A3 + AS15 +/- Poly IC:LC administration	•	•	•	•	•	•	•	•	
Treatment conclusion									• ^e

As a convention, 1 month is defined as 4 weeks, i.e., 28 days, during the treatment phase.

- a. The procedures of this visit are also to be carried out in case of relapse or early withdrawal.
- b. To be repeated/performed at any time if clinically indicated.
- c. A pregnancy test must be performed every 3 months for female patients of childbearing potential.
- d. A pregnancy test should be performed at any time during the study if the investigator/patient suspects that pregnancy has occurred.
- e. After concluding visit, patients will be followed-up every 6 months until relapse or for up to 5 years from the first administration of study treatment. Refer to Table 7 for details on the follow-up phase.
- f. 10 mL of blood sample taken for examination of humoral immunity. It may also be used for translational research.
- g. Pictures should be taken document cutaneous recurrences

Table 6. Timing of study visits and the assessments to be performed (Maintenance Phase and Concluding Visit)

6.2.3. Follow-up period

The duration of active follow-up for survival, recurrence and serious adverse events (SAEs) related to study participation and concurrent medications will be up to 5 years from the first

CONFIDENTIAL

study treatment. The procedures described in the table below will be performed for patients having completed study treatment or for patients withdrawing from treatment prior to completion for reasons other than recurrence.

After relapse, annual post-study contacts, e.g., by telephone, will be instituted to follow the patients for survival.

Study phase:	FOLLOW-UP (F1 - F n+1)					
Study visit no.	F1	F2	F3	F4	F5 to Fn ^a	Fn+1
Date of concluding visit (CV) + no. of months	CV+6m	CV+12m	CV+18m	CV+24m	CV+... ^a	60 m
Safety assessments						
pIMD recorded	•	•	•	•	•	•
Serious adverse events related to study participation and GSK concomitant medications recorded	•	•	•	•	•	•
Laboratory assays						
Blood samples taken for: Humoral immunity ^c		•				
Efficacy assessments						
Neck, chest, abdomen and pelvic CT	•	^b	•	^b	•	•
Physical examination	•	•	•	•	•	•

Months are here defined as calendar months.

- a. These visits will be started 6 months after the concluding visit (whether the patient completed the scheduled 13 injections or was withdrawn from the study treatment before completion) and will be repeated every 6 months until 5 years after first study treatment administration are reached.
- b. To be repeated at any time if clinically indicated..
- c. 10 ml of blood sample taken for examination of humoral immunity. It may also be used for optional translational research.

Table 7. Timing of study visits and the assessments to be performed (Follow-up Phase)

